3.3 Study design

This study will be performed as a prospective single center double blinded randomized controlled trial.

Patients suffering from esophageal cancer scheduled for surgery in curative intent will be randomised to two groups.

Patient Selection and Recruitment

All patients will be treated interdisciplinary by oncologists and surgeons and all patients are being discussed in our interdisciplinary tumor conference. The patients for the study will be screened for eligibility when the decision for curative esophagectomy is made in our "Tumorboard". Recruiting of the patients is performed during the first surgical consultation and after the determination of the further procedures. During this consultation, the planned esophagectomy and the intervention, the risks as well as the aim and purpose of the study is explained to the patients. Furthermore, the eligibility to participate in the study is assessed. In a second consultation which takes place shortly before surgery, patients can provide the informed consent to participate in the study or not.

Randomization and Blinding

If a patient does not provide informed consent he is excluded from the study and will be treated according to the current gold standard and will then receive surgical therapy without additional intervention.

Enrolled patients will be randomized 1:1 into the intervention group and into the control group using the RedCap randomization tool designed in our RedCap database for the study. Group one will be the intervention group. In this group patients will receive an intraoperative endoscopic balloon dilatation of the pylorus by an experienced gastroenterologist before the gastric conduit is formed. Group two will be the control group where the participants will undergo standard surgical resection without intraoperative balloon dilatation of the pylorus. The outcome assessors in this study are the ward physicians, who record the output of the nasogastric tube and record complications and the radiologists who evaluate the X-rays taken. These medical professionals are blinded for the group assigned. In the surgical reports it is only recorded "Esophagectomy Ivor Lewis WIDE Trial". Therefore, the outcome assessors are not able to tell if a patient received the additional intervention or not. The data is then, if possible automatically or by hand transcribed into the RedCap database.

Data Collection

After inclusion into the study, baseline data will be collected and stored in a study-specific Redcap Database. This Redcap Database fulfills all regulations for a study database. In a next step after the operation, surgery-specific data is collected and stored into the redcap database. The surgical reports will not show whether a patient has received an intervention or not. The relevant information concerning the postoperative course of each patient are retrieved from the specific patient charts. These data are collected by ward physicians who do not have access to the study documents and therefore do not know which group the patients were randomized into. After 5 and 10 days, a radiological X-ray of the chest is performed to assess the width of the gastric tube. After 5 and 10 days we also assess whether a nasogastric

tube is in place and, if so, how high the output of the nasogastric tube is. After 3 months we assess the DGCE specific symptoms using the DGCE symptom orientated questionnaire. We also perform a radiological swallow study to record signs, such as delayed contrast passage for late DGCE. Additionally, patients are asked to fill out the EORTC QLQ-OES18 questionnaire to have a more detailed assessment concerning general GI symptoms.

Safety and Unblinding

In case of adverse events, unblinding will be permissible, and procedures for revealing a participant's allocated intervention will be allowed during the trial, also in case of suspension or premature study termination. Unblinding is done by the Surgeon who attended the operation and is therefore not blinded to the group assignment.

3.4. Study intervention

For patients in the intervention group, a balloon catheter will be inserted in the pylorus under gastroscopy guidance during the operation while the patient is in general anesthesia for the esophagectomy by an experienced gastroenterologist. The intervention will be performed intraoperatively before the gastric conduit is formed. The pylorus is then dilated to a predetermined size of 30 mm using a standard balloon dilatation kit. The intervention is carried out according to the standard techniques used by our gastroenterologists and presents the current gold standard in the therapy of DGCE. Hence our gastroenterologists are experienced in performing this intervention. The study intervention will only minimally affect the patient since the only addition for the study is the gastroscopy with balloon dilatation of the pylorus. The time for this intervention is around 20 – 30min additionally.

4 STUDY POPULATION AND STUDY PROCEDURES

4.1 Inclusion and exclusion criteria, justification of study population

Participants fulfilling all of the following inclusion criteria are eligible for the study:

Inclusion criteria:

- Age >18 years
- Histologically confirmed esophageal cancer
- Planned surgical resection in curative intent as a minimally invasive Ivor Lewis procedure
- Provided informed consent

Exclusion criteria:

- Prior esophageal or gastric resection
- Noncurative intent of surgery
- ASA Score V
- Patients lacking capacity to provide informed consent

4.2 Recruitment, screening and informed consent procedure

All patients are presented to our interdisciplinary "Tumourboard" at the Claronis University Digestive Healthcare Center after being diagnosed with esophageal cancer. The further treatment procedure is then determined. If a curative treatment procedure with surgery is determined, the patient's suitability for participation is reviewed in a second step. The potential participants are then invited to our surgical consultation. The patient will be informed about the further procedure and the operation. Patients are also given comprehensive information about the study. The consultation will be performed by one of our surgeons from the department specializing in upper gastrointestinal surgery.

The surgeon will explain to each participant the nature of the study, its purpose, the procedures involved, the expected

duration, the potential risks and benefits and any discomfort it may entail. Each participant will be informed that the participation in the study is voluntary and that he or she may withdraw from the study at any time and that withdrawal of consent will not affect his or her subsequent medical assistance and treatment.

The participant will be informed that his or her medical records may be examined by authorised individuals other than their treating physician. All participants for the study will be provided a participant information sheet and a consent form describing the study and providing sufficient information for participant to make an informed decision about their participation in the study. The patients are then granted between 2 to 8 weeks to think about their consent to participate in the study. During this time the neoadjuvant therapy is administered by our oncologists in the most cases. In a second consultation which takes place shortly before the operation and after the assessment of the anaesthesiologist, patients can provide the informed consent to participate in the study or not after they had sufficient time to make an informed decision. The formal consent of a participant, using the approved consent form, will be obtained before the participant is submitted to any study procedure.

The consent form will be signed and dated by the investigator or his designee at the same time as the participant sign and if informed consent is signed this will be noted in the consultation report. A copy of the signed informed consent will be given to the study participant. The consent form will be retained as part of the study records.

The investigator or the sponsor notifies the Ethics Committee of the first study participant, in accordance with art 62 lit. c ClinO, resp. art 38 ClinO. If the first participating person is not included in the trial within two years following the issuance of the authorization, the trial is considered interrupted (art. 23a ClinO). The clinical trial may not be commenced until an application for an extension of the time limit has been approved. The application for the extension is submitted to the CEC as a substantial amendment.

4.3 Study procedures

The study is planned to take place over a duration of 30 months. We perform between 50 to 70 Esophagectomies per year at Clarunis University Digestive Healthcare Centre, with an estimated participating rate of 80 to 90% we should achieve to include 116 patients in around 30 months. Due to the low risk intervention with minimal side effect for the patient, a high participation rate is expected. We plan to start including patients from December 2025. The study starts for each patient from the time when informed consent is provided. The study follow upends after 3 months postoperatively, when we see the participants for a routine check and perform a radiological passage. After completing the last questionnaire 3 months postoperatively, the collection of the requested data is over. Then patients will enter the usual follow-up care program for esophageal cancer. After randomization into the two groups, group one will be the intervention group. In this group, patients will receive intraoperative balloon dilatation of the pylorus by an experienced gastroenterologist. Group two will be the control group where the participants will undergo standard surgical resection without intraoperative balloon dilatation.

For patients in the intervention group a balloon catheter will be inserted under gastroscopy guidance into the pylorus during the operation via the oral way by an experienced gastroenterologist. The intervention will be performed at the beginning of the surgery, before the gastric conduit is formed. The pylorus is then dilated to a predetermined size of 30mm using a standard balloon dilatation kit. Dilatation to 30 mm is the standard treatment for DGCE and was selected in consultation with our gastroenterologists. This intervention will alter the normal operative course only minimally. The only additional step is the pylorus dilatation by an experienced gastroenterologist which requires 20 – 30min of time. Complications are not to be expected since balloon dilatation of the pylorus is a safe and frequently performed procedure (23). In case of a perforation or bleeding, the problem can immediately be treated by the gastroenterologist or the surgeon. For the patient, no additional harm or discomfort will arise since he/she are under general anaesthesia

for the planned esophagectomy already. In short, the potential harm for the patient undergoing the study intervention is minimal.

After the operation all patients are treated according to our internal guidelines for esophageal surgery. Among other things, the guidelines set out standard procedures for oral liquid and food intake, supportive medication, drainage management and gastric tubes. If the course of treatment deviates from the standard, any necessary therapy is adapted according to the patient's needs in consultation with senior physicians. Postoperatively all patients will be transferred to the Intensive care unit for monitoring. The physicians in charge of the intensive care unit then decide when a transfer to the surgical ward can take place. All patients are supported by our physiotherapist as well as our team of nutritionists. We plan to collect the required data as follows. Surgery-specific data is collected using the information from the clinical information system. These include the duration of the operation, intraoperative complications, details of intraoperative balloon dilatation and anaesthesiologic specialties. The relevant information concerning the postoperative course of each patient are retrieved from the specific patient charts. These data are collected by ward physicians who do not have access to the study documents and therefore do not know which group the patients were randomized into. These data include for example gastric tube and chest tube output, interventions and complications, first bowel movement, time of first solid food intake, days of hospitalization and days spend on the intensive care unit as well as data from postoperative imaging. On the 5th and 10th day we carry out a radiological X-Ray examination of the chest assessing the width of the gastric tube and if the width of the tube is increased in comparison to the baseline X-Ray. Furthermore, we assess the output of the nasogastric tube in millilitres. After 3 months every patient will be seen in our surgical consultation for a routine check-up. There the patients will fill out the DGCE Symptom orientated questionnaire (10) as well as the EORTC QLQ-OES18 questionnaire to assess the Gastrointestinal related Quality of life. In addition, we perform a radiological passage examination to assess the presence of late DGCE. These questionnaires, which are completed on days 5 and 10 as well as after 3 months, together with the radiographic examinations performed at the same time points, represent additional study-specific assessments. They would therefore not be performed in case of non-participation in the study.

4.4 Withdrawal and discontinuation

Patients who withdraw consent and also withdraw of permission to collect further clinical information will be included in the intention-to-treat analysis, but no study-specific follow-up will be performed. All participants who withdraw from the study are no longer involved in the study and no further data collection is performed. If a participant refuses to participate in the study after the hospitalization the participant will be included in the intention to treat analyses. If a patient withdraws the informed consent before the surgery is performed the participant will be excluded from the study.

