Appendix 1: Schedule of assessments

Study Periods	Screening		In-hospital			Follow up
Days	-X	-14	0	5	10	3 months
Patient Information and Informed Consent		+				
Demographics	X	X				
Medical History	X	X				
In- /Exclusion Criteria	+	+				
Physical Examination	X	X	X	X	X	X
Vital Signs			X	X	X	X
Randomisation		+				
Surgery			X			
Primary Outcome				+	+	
Output Nasogastric tube				X	X	
Radiological passage						+
Radiological Chest X-Ray			X	+	+	
Secondary Outcomes				X	X	X
Adverse Events			X	X	X	X
Quality of life (EORTC QLQ-OES18)		+				+
DGCE Questionnaire		+		+	+	+

Symbol explanations:

X: Routine Examinations in all Esophagectomy patients

+: Study specific/additional Examinations

WIDE TRIAL - CONSORT Flowchart

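### Section 4.4 stops all data collection for every participant who withdraws, including those who have not refused use of their clinical records, so routine outcomes of patients kept in the intention-to-treat analysis are discarded

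*Protocol*

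**What the plan says.** Protocol section 4.4 has four rules.

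- First: "Patients who withdraw consent and also withdraw of permission to collect further clinical information will be included in the intention-to-treat analysis", with the rider "but no study-specific follow-up will be performed".
- Second: "All participants who withdraw from the study are no longer involved in the study and no further data collection is performed".
- Third: "If a participant refuses to participate in the study after the hospitalization the participant will be included in the intention to treat analyses".
- Fourth: "If a patient withdraws the informed consent before the surgery is performed the participant will be excluded from the study".

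Section 4.3 gives the source of the postoperative data: "The relevant information concerning the postoperative course of each patient are retrieved from the specific patient charts". It then lists examples: "These data include for example gastric tube and chest tube output, interventions and complications, first bowel movement, time of first solid food intake". It adds that the radiographs and questionnaires at days 5 and 10 and at 3 months are extra to normal care.

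The key to Appendix 1 reads "X: Routine Examinations in all Esophagectomy patients". Nasogastric output on days 5 and 10, the secondary outcomes row and adverse events carry that mark. The day 5 and 10 chest X-rays, the 3-month radiological passage and the questionnaires are marked as study-specific. Section 6.2 requires every participant with a reported adverse event, serious or not, to be followed to full recovery. Section 5.1 sets intention to treat as the analysis principle.

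**The concern.** Leaving study procedures and refusing further use of one's records are different acts, and the first sentence of 4.4 names them separately. The second sentence then applies one consequence, a complete stop, to everyone. A patient who leaves after surgery but would let the hospital's own records be used is treated like one who refuses that use.

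Such a patient has been randomised and operated on. Only withdrawal before surgery leads to exclusion, so the patient remains in the intention-to-treat set without outcomes that the ward records anyway. A SAP can choose how to handle missing values, but it cannot restore data that the protocol said not to collect. The second sentence also conflicts with the adverse-event follow-up in 6.2.

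**Working it through.** **1. Who is affected.**

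| Time and type of withdrawal | In the ITT analysis? | Loss caused by the second sentence |
|---|---|---|
| Before surgery | No (fourth rule) | None; a separate matter |
| Surgery to discharge, chart use not refused | Yes (section 5.1; not excluded by 4.4) | Chart outcomes from that day on |
| Surgery to discharge, chart use refused | Yes (first rule) | None that could be avoided |
| After hospitalisation | Yes (third rule) | Later chart information only; in-hospital data already held |

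The second row is the point. Section 4.4 does not name this group. Its place in the ITT set follows from 5.1 and from the fourth rule excluding only withdrawals before surgery. The primary endpoint is touched only if withdrawal comes before the day 5 and 10 assessments are complete.

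**2. What the chart could still supply.** Five of the seven secondary endpoints in the synopsis: leak, complications, stay, bowel movement and solid food. The other two, late DGCE and quality of life, need study-specific assessments. Section 3.2 defines early DGCE as nasogastric output above 500 ml and/or more than 100% widening on X-ray. High output alone therefore establishes a case. Low output, or no tube, without an X-ray leaves the patient undetermined.

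**3. The plan's own figures.** Inputs from 5.1: 48% v 22%, alpha 0.05 (taken as two-sided), power 80%, attrition 10%. The mean rate is 0.35.

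n = [1.960·√(2·0.35·0.65) + 0.842·√(0.48·0.52 + 0.22·0.78)]² / 0.26² = 51.6, so 52 per arm. Then 52/0.9 = 57.8, so 58. Both figures reproduce. Power is 80.3% with 52 evaluable per arm and 84.5% with 58.

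**4. How far missing outcomes could move the result.** Let m of 58 per arm be missing, with planning rates in the rest. The extreme bounds on the risk difference over all randomised patients are [0.26·(58 − m) ± m]/58:

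- m = 1: 0.238 to 0.273
- m = 3: 0.195 to 0.298
- m = 4: 0.173 to 0.311
- m = 6: 0.130 to 0.337

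In whole patients, counting every missing intervention patient as an event and every missing control patient as none:

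| m per arm | Control | Intervention | Chi-square p | Fisher p |
|---|---|---|---|---|
| 1 or 2 | 27/58 | 14/58 | 0.012 | 0.019 |
| 3 | 26/58 | 15/58 | 0.033 | 0.051 |
| 4 | 26/58 | 16/58 | 0.053 | 0.082 |
| 6 | 25/58 | 17/58 | 0.12 | 0.18 |

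For m = 6 the observed data are 25/52 v 11/52 (chi-square p = 0.004), and the opposite filling gives 31/58 v 11/58 (p = 0.0001). Section 5.1 allows either test; chi-square is the natural one at these counts.

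**The case against.** Three stronger readings are tempting, and the documents do not support them.

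- **Declining X-rays or questionnaires ends chart collection.** A reader might infer this, but the second sentence covers participants who withdraw from the study. Nothing in 4.4 makes refusal of a single assessment a withdrawal.
- **The rule could swing the result from p = 0.12 to p = 0.0001.** That range puts the whole 10% allowance between surgery and day 10, and p = 0.12 needs 6 of 6 events in one arm and 0 of 6 in the other. The allowance covers dropout and loss to follow-up over the whole study. Some of it will be patients who leave after discharge, or who refuse chart use and would be lost under any wording.
- **The rule costs the primary endpoint, and chart data would restore it.** The day 5 and 10 X-rays stop at withdrawal anyway. The chart can then yield positives only, which is one-sided ascertainment and must be treated as such.

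It can also be said that the first sentence describes a single group who withdraw both things, that a full stop is a cautious privacy choice, and that missing-data handling belongs in a SAP. The consent pages are not in the file, so they may already separate levels of withdrawal. These points limit the size of the concern but do not remove it. The second sentence says all participants, staff would follow it literally, and it contradicts 6.2. That patients with a hard course withdraw more often is plausible, but nothing in the protocol shows it.

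**Conclusion.** The point stands as an avoidable loss of data and an internal conflict, of moderate weight. For patients who withdraw between surgery and discharge without refusing chart use, the second sentence of 4.4 discards five chart-based secondary endpoints, adverse events and the nasogastric part of the primary endpoint.

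The number of such patients is not given and is probably well below 6 per arm. Under planning rates and worst-case filling, the chi-square result holds to about 3 missing per arm and is lost at about 4; Fisher's test is already borderline at 3. These are bounds on what missing outcomes could do. They are not estimates of harm from this rule, and not all of the missing outcomes would be recovered by changing it. The sample size is unaffected.

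**What to change.** Replace the second sentence of 4.4 with: *A participant who withdraws has no further study-specific assessments (marked + in Appendix 1). Routine clinical data continue to be collected from the chart up to 3 months unless the participant also withdraws permission for this.*

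In addition:

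- Ask for the level of withdrawal, record it and its date in REDCap, and align the consent wording.
- Reconcile 4.4 with the adverse-event follow-up in 6.2.
- State that, without the study X-rays, chart data can confirm early DGCE by nasogastric output but cannot exclude it. A patient with low or no output and no X-ray stays missing or undetermined for the primary endpoint and is not counted as DGCE-free.

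Cost: one extra question at withdrawal, one REDCap field, and a protocol and consent amendment with ethics approval. No procedure or patient is added. Recovery of the primary endpoint is only partial. The change works only prospectively, so it should be made early.

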5 STATISTICS AND METHODOLOGY

5.1. Statistical analysis plan and sample size calculation

The aim of this power analysis was to calculate the minimum required sample size for our randomized controlled trial (RCT) investigating the effect of intraoperative endoscopic pyloric dilatation on the incidence of early delayed gastric conduit emptying (DGCE) within the first 14 days after esophagectomy.

The sample size calculation for this study was based on findings from Boshier et al. (18), which demonstrated a reduction in the incidence of DGCE from 48% to 22% following intraoperative pyloric stretching procedures. To achieve a statistical power of 80% ($1 - \beta = 0.80$) while maintaining a Type I error rate of 0.05 ($\alpha = 0.05$), a power analysis for comparing two independent proportions was performed. The absolute difference in proportions (Δ) was set at 26 (0.48

- 0.22). Using these parameters, the required sample size was calculated to be 52 patients per group, resulting in a total of 104 patients for the study. This ensures sufficient power to detect a statistically significant difference in DGCE incidence between the two treatment groups.

To account for potential dropouts or loss to follow-up, an estimated attrition rate of 10% was considered. Consequently, the final target enrolment is increased to 58 patients per group, leading to a total of 116 patients. This adjustment maintains adequate statistical power even if a subset of participants does not complete the study.

The statistical analysis will be conducted according to the intention-to-treat (ITT) principle. Categorical variables will be analyzed using Chi-square or Fisher's exact test, while continuous variables will be evaluated using either independent t-tests or Mann-Whitney U tests, depending on the distribution. Multivariable logistic regression analysis will be used to adjust for relevant covariates and potential confounding factors.

All statistical analyses will be performed in collaboration with an experienced statistician from our research group using validated software such as SPSS or R. A significance level of $p < 0.05$ will be considered statistically significant for all tests.

